Based on data from Mali suggesting that doses higher than 20mg/kg are needed to protect for 12 months, we propose to assess the safety of an additional two doses: 30 mg/kg and 40 mg/kg in a similar fashion. This extension of part 1 will include an additional 24 children, and will utilize a similar design to before, with 12 participants in each age-dose group in a 3:1 ratio of L9LS to placebo; all participants will be followed for a total of 3 months. However, given that it appears that the younger children are clearing the product more quickly than older people, we will include only children aged 5-71 months, as these are the ages of the children to be included in the part 2 extension. As before, we will ensure safety out to 7 days before proceeding to dose additional subjects.

Part 2: Efficacy study

A total of 324 children 5-59 months of age will be randomized to receive a 10-20 mg/kg dose of L9LS or placebo by SC administration. There will be two L9LS cohorts, one 5-17 months of age and another 18-59 months of age, which will constitute one L9LS arm. A placebo arm will be composed of children 5–59 months of age. They will be followed over 12 months with monthly blood smear microscopy and polymerase chain reaction (PCR) and twicemonthly symptomatology and care-seeking behavior questionnaires. Dosing will be based on three weight bands; all doses will be administered SC with fixed doses of 75 mg L9LS, 150 mg L9LS, or 225 mg L9LS, resulting in a range of 10-20 mg/kg in a double-blinded fashion. Blood will be drawn to assess antibody titers at baseline, and at three additional time points over 12 months to establish pharmacokinetics (PK). Participants in the L9LS arm will be

randomized 1:1 at baseline to receive either a second L9LS injection or a placebo injection to evaluate the additional efficacy of a second dose administered 6 months after the first dose. (Those in the placebo arm will receive a second injection of placebo.) Participants will be followed for an additional 6 months after the second injection with monthly blood smear microscopy and PCR, and a blood draw at month 11 to assess L9LS PK.

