² At any time during the study, the subject may have an unscheduled illness visit if experiencing malaria symptoms or other symptoms. The subject may be referred for standard care according to local guidelines.

³ Complete/comprehensive at screening; targeted/interim at other visits.

⁴ The first dose of dihydroartemisinin-piperaquine will be directly observed in the clinic if possible, but might be given in the participant's home. The subsequent 2 doses given over the following 2 days will be observed by guides in the subject's home or at the clinic. All dihydroartemisinin-piperaquine doses will be completed prior to day 0 and will be initiated between 21 and 14 days prior to D0.

⁵ L9LS or placebo. All other study procedures must be completed prior to study agent administration. Subjects who received L9LS at day 0 will receive L9LS or placebo at month 6; those in the placebo arm will receive a second placebo injection at 6 months. Each subject will be monitored for at least 60 minutes after study agent

administration and vital signs will be recorded 1 hour after study agent administration. Prior to discharge, subject will be assessed for local reactogenicity (including pain/tenderness, swelling, redness, bruising, and pruritus at the site of injection) and systemic reactogenicity (including fever, feeling unusually tired or unwell, muscle aches, headache, chills, nausea, and joint pain). If the subject is assessed as being unwell or has ongoing reactogenicity symptoms, he or she will be asked to remain in the clinic until evaluation and discharge by a study clinician. Clinicians will follow any solicited symptoms that are ongoing until they have resolved.

⁶ Viral screenings will be performed according to international guidelines. HIV testing will be 2 rapid diagnostic tests (RDTs), plus DNA PCR if the RDTs are discordant; subject will be referred for medical care for 2 positive RDTs or a positive PCR. Pre- and post-test HIV counseling will be provided.

⁷ EDTA tube will be stored at screening, and hemoglobin typing will be performed; in the rare case that hemoglobin typing detects sickle cell disease, the participant will be considered a late screening failure; sickle cell trait is not an exclusion criterion.

⁸ Collected prior to study agent administration. Other indicated tests may be performed after study agent administration.

⁹ For PK, 3.5 mL serum will be collected prior to malaria treatment administration.

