The CDC has collaborated with KEMRI in western Kenya to evaluate tools for malaria transmission and burden reduction for over 40 years. The collaboration has a highly experienced clinical trials unit that includes two pediatricians, immunologists, medical officers, pharmacists, clinical officers, nurses, quality control and regulatory officers. This group has been involved in phase 2, 3, and 4 trials of RTS,S/AS01 and conducted the largest phase 2 trial of the PfSPZ Vaccine in 5- to 12-month-old infants as well as a number of pharmaceutical clinical trials. The clinical trials unit is based in Siaya County Referral Hospital, the largest hospital in Siaya County, western Kenya. Here, malaria transmission is perennial with seasonal peaks following the long and short rains in June/July and November/December, respectively. Clinical malaria incidence (any parasite density by microscopy in a child who reports fever within the previous 24 hours) among children aged 5 to 17 months was 3.06 cases per year in 2019–2020. In the recent PfSPZ Vaccine trial among infants 5-12 months of age at the time of first vaccination (with a 3-dose series over 5 months), 66.7% of participants in the placebo arm had at least one Pf infection based on microscopy within 6 months after the last dose; in another trial among 5- to 17-month-olds at the time of first vaccination (with a 3-dose series over 3 months), 46.8% had at least one clinical malaria episode (parasitemia >0 parasites/µL and fever/history of fever within 24 hours) within 6 months after the last dose. Currently, the RTS,S/AS01 malaria vaccine is being rolled out by the Kenya Expanded Programme on Immunization in select sub-counties in western Kenya; the RTS,S/AS01 vaccine is not being implemented in Alego-Usonga sub-county (where the clinical research site is located). The current Malaria Vaccine Pilot Evaluation is scheduled to run until May 2023, so the earliest that RTS,S/AS01 vaccinations would be offered in Karemo, where the study site hospital is, would be June 2023. In part 2, staff will also recruit and follow up patients at Kogelo Dispensary, a satellite clinic referring patients to Siaya County Referral Hospital.

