8.2.3 Correlative Studies for Research/Pharmacokinetic Studies

The following evaluations will be performed according to the schedule presented in section 0.

Blood smear: Thick and thin blood smears will be prepared and analyzed by the standard WHO method (section 2.2.2.3) to identify Pf infection for the primary endpoint and to identify clinical malaria for a secondary endpoint. This evaluation will be performed within 48 hours of collection, unless the subject is displaying signs or symptoms of clinical malaria in which case the blood smear will be analyzed at the time of the scheduled or unscheduled visit. For

asymptomatic participants with positive blood smears, a home visit will be conducted within 72 hours of the blood draw to notify the family and provide treatment.

Pf RT-PCR: RT-PCR will be performed to identify Pf infection as a secondary endpoint. This evaluation will be performed at the University of Washington in the US on coded dried blood spots. Real-time PCR might also be performed by KEMRI on the dried blood spots.

PK studies: Blood L9LS concentrations will be measured by Meso Scale Discovery LLC-based automation platform. The concentration at the visit prior to the first Pf infection will be used to assess L9LS-mediated protection. This evaluation will be performed at the NIAID.

ADA detection: Assays for detection of ADA will be performed at specified timepoints (section 0) following product administration and compared to baseline status. This evaluation will be performed at the NIAID.

Parasite genotyping: For subjects who become infected during the study, coded blood samples collected around the time of the first infection will be used to perform a genotypic sieve analysis to analyze sequences of breakthrough parasites (section 9.5.11). This evaluation will be performed by [name] at the Harvard School of Public Health.

Pf-specific antibodies: Levels of antibodies specific for pre-erythrocytic and blood-stage Pf antigens will be measured by NIH in stored serum samples collected at enrollment and at one of the subsequent blood draws to explore the impact of L9LS on naturally acquired humoral immunity to malaria.

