To assess the association of L9LS concentration with protection, we will perform a Cox proportional hazards regression for the time to the first infection with L9LS concentration as a time-varying covariate. A logistic regression analysis will be additionally performed to model the infection rate as a function of L9LS concentration using generalized estimating equation to account for repeated measures. This analysis will be performed over all participants that receive L9LS including those aged 5-10 years in the dose-escalation study and those in the efficacy study.

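### The repeated-measures logistic model of infection on L9LS concentration (9.5.6) names no term for visit, season, age or study part, so it can show a concentration effect when none exists

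*Combined protocol and SAP*

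**What the plan says.** Section 9.5.6 names two models for secondary objectives 7a and 7b. The first is a Cox model: "we will perform a Cox proportional hazards regression for the time to the first infection with L9LS concentration as a time-varying covariate". The second is the GEE logistic model: "A logistic regression analysis will be additionally performed to model the infection rate as a function of L9LS concentration using generalized estimating equation", with GEE used to handle repeated measures. The analysis set is "all participants that receive L9LS including those aged 5-10 years in the dose-escalation study and those in the efficacy study". Neither model names a regressor other than concentration.

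On which concentration is linked to infection, 8.2.3 says: "The concentration at the visit prior to the first Pf infection will be used to assess L9LS-mediated protection". The part 2 draws are few: "Blood will be drawn to assess antibody titers at baseline, and at three additional time points over 12 months". The schedule in 1.4.2 places them at baseline, D28, D196 and D336, and the baseline draw precedes any L9LS ("For PK, 3.5 mL serum will be collected prior to malaria treatment administration"). Section 9.5.6 also plans a two-compartment population PK model, but does not say that its predictions feed the protection models.

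Section 9.5 promises a detailed SAP, written before unblinding, that will take precedence over the protocol.

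**The concern.** GEE deals with correlation within a child. It does not remove confounding between concentration and anything else that changes from visit to visit. Here several things do:

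- **Time since dose.** The half-life in Malian children is about 35 days (4.2.2), so level falls steeply with follow-up.
- **Interval length.** In part 2, smears at D7 and D175 come 7 days after a dose, and those at D28 and D196 come 21 days later; other intervals are 28 days (1.4.2). Part 1 smears are weekly to D28 (1.4.1). Intervals are therefore shortest when levels are highest.
- **Antimalarial.** DP starts 14–21 days before dose 1. None is scheduled before the month-6 dose in part 2 (1.4.2).
- **Season.** At the site "malaria transmission is perennial with seasonal peaks following the long and short rains in June/July and November/December".
- **Age and part.** Part 1 includes children aged 5–10 years and stops at 3 months, so it contributes only early post-dose visits.

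At stake is the concentration–risk relation itself. Section 4.2.2 says the range of levels should help determine a protective titer. A slope made up partly of between-visit differences in background risk would mislead that work.

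**Working it through.** **No figure to reproduce.** Section 9.5.6 states no sample size or power for this analysis. To confirm the background rate used below, I checked Table 6. For 35% vs 10.5% at 80% power, the unpooled two-proportion formula gives (1.960 + 0.842)² × (0.35×0.65 + 0.105×0.895) / 0.245² = 7.85 × 0.3215 / 0.0600 = 42.0, which rounds up to the stated 43.

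**How closely level follows time.** Section 4.2.2 gives a half-life of 35 days and 243 days to reach 0.61 µg/mL. Back-extrapolation gives C0 = 0.61 × 2^(243/35) ≈ 75 µg/mL. With C(t) = 75 × 2^(−t/35):

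| Day | One dose | Second dose at D168 |
|---|---|---|
| D28 | 43 | 43 |
| D196 | 1.5 | 43 + 1.5 ≈ 45 |
| D336 | 0.10 | 2.7 + 0.1 = 2.8 |

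**How interval length alone matters.** With 35% infected by 24 weeks (9.2.2), the weekly hazard is −ln(0.65)/24 = 0.018. The risk per interval is 1 − exp(−0.018 × weeks): 1.8% for 7 days, 5.2% for 21 days and 6.9% for 28 days. A per-visit logistic model with no interval term reads the shorter intervals at high levels as lower risk.

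**Simulation with no concentration effect.** There were 216 part 2 recipients (half re-dosed at week 24) and 54 part 1 recipients, with 550 runs per scenario. The Monte Carlo SE at 5% is √(0.05×0.95/550) ≈ 0.9 points. These inputs are assumptions, not in the documents: first-4-week risk ratio of 1, 0.5, 0.25 or 0.05; between-child concentration SD of 0.3 on the log scale; frailty SD of 0.3; seasonal peak ratio of 2 where used; uniform 26-week accrual.

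Concentration assigned at each visit interval:

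| Scenario | Plain GEE: OR per 10-fold | Plain GEE: false positives | GEE + visit + part | Cox, time since dose 1 |
|---|---|---|---|---|
| Ratio 1 | 0.91 | 17% | 5% | 4% |
| Ratio 0.5 | 0.84 | 37% | 6% | 5% |
| Ratio 0.25 | 0.81 | 53% | 7% | 3% |
| Ratio 0.05 | 0.78 | 67% | 5% | 6% |
| Ratio 1, season 2 | 0.88 | 33% | 4% | 4% |
| Ratio 0.25, season 2 | 0.79 | 77% | 6% | 2% |

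With visit and part terms the OR is 0.99–1.00 in these rows. Halving risk at ages 5–10 left the plain GEE at 17% and the Cox model at 5%.

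Last actual draw carried forward, so that the pre-dose zero covers visits up to D28:

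| Ratio | Plain GEE: OR per 10-fold | Plain GEE: false positives |
|---|---|---|
| 1 | 1.01 | 6% |
| 0.5 | 1.10 | 17% |
| 0.25 | 1.16 | 32% |
| 0.05 | 1.20 | 45% |

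At ratios below 1, almost none of these false positives are in the protective direction. The Cox model under this rule gave 3–7%.

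**Sensitivity to set-up.** A simulation of part 2 alone gave 10–40% for the plain GEE, and 5–10% with visit terms. Another used only the D28, D196 and D336 samples with equal 28-day risk windows. It gave 5%, 11%, 24–34% and 50–73% when risk after D28 was 100%, 75%, 50% and 25% of later risk, and 4–7% with visit as a factor. With equal windows and constant risk, the error is therefore nominal.

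**The case against.** The strongest reply has four parts.

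1. The Cox model is listed first and the logistic model is an addition. On a time-since-first-dose scale, Cox risk sets compare children at the same follow-up time, so an early low-risk period cannot pass as a concentration effect. This stands. A reader might infer that the whole concentration–protection analysis is compromised. The evidence does not support that, although 9.5.6 does not state the Cox time scale.
2. No passage says that risk is low in the first month, and 2.3.1 gives DP's purpose only as clearing existing infection. This also stands. The early risk ratios are assumptions. The 17% figure needs none of them, because it arises with constant risk and the trial's unequal intervals.
3. The direction is not fixed. A reader might infer that the model will flatter L9LS. Under a literal last-draw reading of 8.2.3 it does the reverse. This stands, and it adds a gap: an unstated rule decides the sign of the bias.
4. Leaving covariates unnamed does not exclude them, and a SAP is to follow. However, 9.5.4 does name time of enrollment for the adjusted efficacy Cox model, and handles prior events and post-treatment time for recurrent episodes. Nothing comparable is carried into 9.5.6. The later SAP is the place for the fix, not evidence that it has been made.

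**Conclusion.** The concern holds for the GEE logistic model only. Fitted as written, it can show a concentration effect when none exists. With concentration assigned at each visit interval, false positives are about 10–17% with no low-risk period and about 25–65% for assumed first-month risk ratios of 0.5 to 0.05, against the two-sided 5% in 9.5.1. The exact size depends on those ratios and on the simulation set-up, and the direction depends on the assignment rule. The Cox model on time since first dose is not shown to be affected.

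This is a supplementary model for a secondary objective with no decision rule attached, so no primary conclusion of the trial is at risk. It should still be corrected, because the remedy is cheap and the relation it estimates is one the trial set out to learn.

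**What to change.** In 9.5.6, or in the SAP before unblinding:

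1. Add to the GEE model scheduled visit (or time since first dose together with interval length), calendar time, age group and study part.
2. State how concentration is assigned at visits without a draw, for example as population-PK predictions for each interval or as the last measured value. Include the handling of values below the assay limit; 9.5.6 sets these to zero for AUC only.
3. State that the Cox model uses time since first dose.

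Two further changes may come to mind: adding placebo children at zero concentration, or analysing part 1 on its own. I do not recommend either. Zero has no value on a log scale, the placebo contrast would drive the slope and is already estimated in 9.5.4, and part 1 alone has 54 recipients followed for 3 months.

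The cost is wording plus wider intervals, because between-visit differences no longer count as evidence. The model stays estimable: the randomised second dose separates levels at the same visit (about 45 vs 1.5 µg/mL at D196 in the calculation above).

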9.5.7 Baseline Descriptive Statistics

Treatment arms will be compared for baseline subject characteristics using descriptive statistics. For continuous variables, the mean or median will be calculated for each treatment arm. For categorial variables, the proportion under each category will be calculated for each arm.

9.5.8 Planned Interim Analyses

Interim safety analysis will be performed when safety data are available from the age deescalation and dose escalation study subjects, starting at least 7 days after the last participant in part 1 receives their antibody (or placebo) dose. The purpose of the interim analysis on safety data is to clear safety concerns for proceeding to the efficacy study.

An interim efficacy analysis will be conducted when clean data are available for all participants through the 6-month endpoint (at 24 weeks). This will assess Pf infection up to 24 weeks by blood smear and clinical malaria using time-to-event analysis and proportional analyses. Having these data available in a timely manner will add to the evidence base needed to plan a potential phase 3 trial of L9LS in settings with seasonal malaria transmission where the time for protection is 6 months. The interim analysis will not impact the conduct of this trial or induce significance level adjustment in the efficacy analyses of this trial.

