6.3.2 Blinding

Parts 1 and 2, as well as the follow-on (part 1 b and part 2 extension), of this trial will be conducted with a double blind. Because L9LS has a slight yellow tint, and the placebo (normal saline) is colorless, the pharmacy team will cover all syringes with transparent yellow tape to maintain blinding for all parts of the study. The subjects, the clinical staff, and the study team will be blinded to study treatment allocation, with the exception of designated individuals who administer the study agents and remain separate from the team of blinded investigators who conduct all subsequent follow-up study assessments. The study pharmacy team will be unblinded, and they are responsible for maintaining security of study treatment assignments.

Data will remain blinded until the last subject completes the final study visit for each phase of the study (part 1, part 1b, part 2, and the follow-on). Blinded subjects will then be informed about their study treatment assignment.

Unscheduled unblinding, either intentional (e.g., in the case of a medical emergency in a subject) or unintentional, will be handled according to SOPs. Intentional and unintentional unscheduled unblinding will be documented in the appropriate source and/or research record and will include the reason for the unscheduled unblinding, the date it occurred, who approved the unblinding, who was unblinded, who was notified of the unblinding, and the plan for the subject.

The principal investigator will report all cases of intentional and unintentional unscheduled unblinding to the DSMB in writing within 1 business day after site awareness via email to the DSMB mailbox ([contact]) outlining the reason for the unblinding and the date it occurred. The report will also be submitted to the IRBs. If an SAE has resulted in unblinding, this information will be included in the SAE Report.

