8.4.4.3.2 Data and Safety Monitoring Board

The NIAID intramural DSMB includes independent experts that do not have direct involvement in the conduct of the study and have no significant conflicts of interest as defined by NIAID policy. The DSMB will review the study protocol, consent documents, and investigator brochure prior to initiation and twice a year thereafter, or as may be determined by the DSMB. Additionally, the DSMB will conduct 1 interim analysis when safety data are available from the dose-escalation study subjects (section 9.5.8).

The DSMB may convene additional reviews as necessary. The DSMB will review the unblinded study data as needed to evaluate the safety, efficacy, study progress, and conduct of the study.

All deaths, SAEs, UPs, and IND safety reports will be reported to the DSMB at the same time they are submitted to the IRBs and CSO unless otherwise specified herein.

All cases of intentional or unintentional unblinding will be reported to the DSMB not later than 1 business day from the time of study personnel awareness.

The principal investigators will notify the DSMB at the time pausing or halting criteria are met and obtain a recommendation concerning continuation, modification, or termination of the study.

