9.5 Statistical Analyses

A detailed study statistical analytical plan for the final analysis, which will supersede the study protocol, will be drawn up during the study before the unblinding of data at database lock.

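### The 24-week efficacy analysis has no stated exception to the Part 2 blind and no named unblinded analyst, and the SAP may be finalised after its by-arm result

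*Combined protocol and SAP*

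**What the plan says.** Four places in the combined protocol and SAP bear on this.

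- **Section 9.5.8 (interim analyses).** "An interim efficacy analysis will be conducted when clean data are available for all participants through the 6-month endpoint (at 24 weeks". On content: "This will assess Pf infection up to 24 weeks by blood smear and clinical malaria using time-to-event analysis and proportional analyses". On purpose: "Having these data available in a timely manner will add to the evidence base needed to plan a potential phase 3 trial of L9LS". On consequences: "The interim analysis will not impact the conduct of this trial or induce significance level adjustment in the efficacy analyses of this trial". It does not say who holds the arm codes for this analysis, who receives the results, or who must not.
- **Section 6.3.2 (blinding).** "Data will remain blinded until the last subject completes the final study visit for each phase of the study". Subjects, clinical staff and study team are blinded, "with the exception of designated individuals who administer the study agents and remain separate from the team of blinded investigators". The pharmacy team is also unblinded. Unscheduled unblinding, such as in an emergency, goes by SOP. The 24-week analysis is not mentioned.
- **Section 9.5 (statistical analyses).** A separate SAP for the final analysis takes precedence over the protocol and "will be drawn up during the study before the unblinding of data at database lock".
- **Section 8.4.4.3.2 (DSMB).** "the DSMB will conduct 1 interim analysis when safety data are available from the dose-escalation study subjects". The board may also look at unblinded safety and efficacy data when it needs to. The 24-week efficacy analysis is not assigned to it.

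**The concern.** The SAP deadline in section 9.5 protects the final analysis only if database lock is the first time anyone sees outcomes by arm. Section 9.5.8 creates an earlier occasion. A SAP completed after the 24-week result would comply fully with section 9.5, and because it overrides the protocol it could settle or change analysis rules with that result in view.

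The second issue is access. The analysis is meant to inform phase 3 planning, which suggests readers beyond the DSMB, yet no boundary is drawn between those readers and the people still assessing children. Some of that assessment involves judgment: the second clinical malaria definition in section 2.2.2.3 accepts a reported history of fever, and adverse-event causality is assigned by the investigator (section 8.4.2.1.2).

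At stake is the credibility of the 52-week efficacy result: whether its rules were fixed without knowledge of the arms, and whether this can be demonstrated afterwards.

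**Working it through.** **1. Are arm codes needed?** Section 9.5.8 does not say that results are by arm. But the efficacy methods in section 9.5.4 (log-rank test, hazard ratio, one minus relative risk) all compare arms, so the analysis cannot estimate efficacy without the codes.

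**2. Who is still in follow-up?** Section 5.7 expects enrolment to both parts within six months, so the first and last Part 2 children are at most about 26 weeks apart. When the last child reaches week 24, the first is at most at week 24 + 26 = 50, and the last has 52 − 24 = 28 weeks to go. Slower accrual or data cleaning would let some children finish first.

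**3. Reproduce Table 6.** Inputs: placebo infected 35% by 6 months and 45% by 12; efficacy 70% and 60%; 80% power; two-sided 0.05. L9LS infected = 0.35 × 0.30 = 10.5% and 0.45 × 0.40 = 18%. With the unpooled formula n = (1.96 + 0.842)² × [p₁(1−p₁) + p₂(1−p₂)] / (p₁−p₂)²:

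- 6 months: 7.85 × (0.2275 + 0.0940) / 0.0600 = 42.0, rounded up to 43.
- 12 months: 7.85 × (0.2475 + 0.1476) / 0.0729 = 42.5, rounded up to 43.

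Both match the table. Doubling gives 86, and 86/0.80 gives 108 per L9LS age group; 43/0.80 gives 54 per placebo age group.

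**4. Share of expected first infections occurring by week 24.** The documents state no such figure. With 108 two-dose L9LS and 108 placebo children:

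- by week 24: 108 × (0.35 + 0.105) = 49.1
- by week 52: 108 × (0.45 + 0.18) = 68.0
- share: 49.1 / 68.0 = **72%** (placebo alone 35/45 = 78%; L9LS alone 10.5/18 = 58%)

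**5. Range.** Comparing all L9LS with placebo (216 versus 108) doubles the L9LS term; Table 6 uses the same 12-month efficacy with and without dose 2.

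| Placebo infected, 6 / 12 months | Efficacy 70% then 60%: two-dose vs placebo | Efficacy 70% then 60%: all L9LS vs placebo | Efficacy 70% at both times |
|---|---|---|---|
| 30% / 40% | 0.39/0.56 = 70% | 0.48/0.72 = 67% | 75% |
| 35% / 45% | 0.455/0.63 = 72% | 0.56/0.81 = 69% | 78% |
| 40% / 45% | 0.52/0.63 = 83% | 0.64/0.81 = 79% | 89% |

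The last column follows the text of section 9.2.2, which gives 70% efficacy at 12 months; the share is then the placebo ratio for either comparison. A common loss rate cancels. Losses spread evenly over the year (my assumption: constant dropout hazard, 20% to 25%) move the 72% to 74% or 75%.

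**6. What is fixed and what is open.** Sections 9.5.1 and 9.5.4 already fix the endpoint (smear-positive infection, Day 7 to week 52), the MITT set, the interval-censored log-rank test and Cox model, the Kaplan-Meier-based secondary analysis and two-sided 0.05. Still open are:

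- the primary comparison: two-dose L9LS versus placebo in section 9.2.2, all children receiving the antibody versus placebo in section 9.5.4;
- covariates in the additional Cox model beyond enrolment time, which depend on observed imbalance;
- the missing-data method, which depends on how much is missing and names imputation and weighting only as examples.

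**The case against.** The best defence is that section 6.3.2 blinds people, not data. It lists who is blinded, and the sentence on data is followed by one about telling blinded subjects their assignment. On that reading an analyst outside the blinded team could run the 24-week analysis and satisfy both sections, much as the DSMB may see unblinded efficacy data before lock. This stands in part. A reader might infer that the interim necessarily breaks the study team's blind; the documents do not support that. What they lack is the procedure that would keep the blind and a sentence in section 6.3.2 allowing for it.

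A reader might also infer that investigators will assess endpoints and adverse events knowing the result. No section says that assessors receive it, arm-level results do not reveal a child's allocation, and routine smears are read by two independent microscopists (section 2.2.2.3). The exposure is possible, not established.

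Finally, section 9.5 has the SAP written during the study, so it may well be signed before week 24, and much of the analysis is already in the protocol. That narrows the freedom left but does not close it: nothing requires the earlier date, and the comparison that defines the primary result is among the open items.

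**Conclusion.** The point holds as a should-fix. The plan sets the SAP deadline at the wrong milestone and leaves a by-arm efficacy analysis without a named analyst, a limit on release, or an exception in the blinding section. On the planning assumptions about 72% of expected first infections (67% to 89%) would be known by arm before the SAP has to exist. This rests on Table 6 infection rates and efficacies, not on observed data.

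The 72% should not be read as the share of the two-dose answer already known. Dose 2 is given at the week-24 visit (section 1.4.2), so the interim says nothing about what the second dose adds. Nor is the absence of a significance-level adjustment an error here: the analysis carries no stopping rule and no adaptation. The statement that the interim will not affect conduct answers those two matters, but not when the SAP is signed or who sees the result.

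**What to change.** 1. **Section 9.5:** require the Part 2 efficacy SAP to be signed before any by-arm 24-week data are produced, with the primary comparison, covariates and missing-data method settled in it.
2. **Section 9.5.8:** have the analysis run by a statistician outside the blinded team, and withhold by-arm results from site staff, microscopists and endpoint and adverse-event assessors until the last Part 2 visit.
3. **Section 6.3.2:** state this analysis as the exception.

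A fallback is needed. Version 6.0 is dated 2 April 2024, and section 1.1 dates the original study to June 2024. If that month marks the last week-52 visit, the last week-24 visit fell 28 weeks earlier, between mid-November and mid-December 2023. The documents do not say whether the analysis has been run. If it has, record the SAP date and who saw by-arm results and when, and label any later SAP decision as made after the interim.

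The cost is wording and earlier sign-off. The SAP falls due sooner, and the site team sees the 24-week results later. Sample size, visits and treatment are unaffected.
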